12.0 Version History

SAP Version History Summary

[figure not shown]
Version	Date	Summary
1.0 Draft	20 AUG 2019	Original draft version prepared for agencies' feedback
1.0	21 SEP 2020	Incorporated agencies' comments

Appendix A. Protocol Deviations

[figure not shown]
Subjects who reported any protocol deviation will be summarized.

Appendix B. Time Windows for Analysis of EQ 5D-5L, EORTC QLQ-C30, and PROMIS Cancer Fatigue SF 7a

Scheduled Visit	Nominal Cycle Rx Day	Time Window (Cycle Rx Day Range)
Baseline	≤ 1	Last non-missing value on or prior to the first dose of study drug for Part 1 or Arm A in Part 2; Last non-missing value on or prior to randomization for Arm B in Part 2
Each Other Cycle from Cycle 3 Day 1	1	[-10, 10]

[figure not shown]
Note: EQ 5D-5L, EORTC QLQ-C30, and PROMIS Cancer Fatigue SF 7a will be assessed at visits specified in the ops manual.

Appendix C. Time Windows for Analysis of Clinical Hematology and Chemistry Parameters

Scheduled Visit	Nominal Cycle Rx Day	Time Window (Cycle Rx Day Range)
Baseline	≤ 1	Last non-missing value on or prior to the first dose of study drug for Part 1 or Arm A in Part 2; Last non-missing value on or prior to randomization for Arm B in Part 2
Cycle 1 Day 8	8	[5, 11]
Cycle 1 Day 15	15	[12, 18]
Cycle 1 Day 22	22	[19, 25]
Cycle 2 Day 1	1	[-3, 3]
Cycle 2 Day 8	8	[5, 11]
Cycle 2 Day 15	15	[12, 18]
Cycle 2 Day 22	22	[19, 25]
Cycle 3 Day 1	1	[-3,10]
Cycle 4 onward Day 1	1	[-10, 10]

Note: Clinical hematology and chemistry samples will be collected at visits specified in the ops manual.

Appendix D. Conversion of leukocyte differential counts from percentage (%) value to absolute value

[figure not shown]
All efficacy and safety analyses will include leukocyte differential values in % and absolute values. The following conversion process will be performed, if sites only provided % values for leukocyte differential counts without absolute counts on the same collection date and time of the total leukocyte counts.

- 1. The conversion is only for leukocyte differential counts in % values which were collected on the same date and at same time as total leukocyte counts.
- 2. Leukocyte differential absolute value ($\times 10^9/L$) = Total leukocyte count ($\times 10^9/L$) \times leukocyte differential value (%)/100
- 3. The following low normal ranges will be used for leukocyte differential counts in % value converted to absolute count values for the shift tables.

Lab Test: Total Leukocytes and differential leukocyte counts	Normal Range (SI units)
Total Leukocyte (× 10 ⁹ /L)	4.5 - 11
Neutrophils (%)	40 - 70
Lymphocytes (%)	22 - 44

^{*}Source: Kratz A et al. Laboratory Reference Values. N Engl J Med 2004; 351:1548-63.

Lower limit of normal of 1.8×10^9 /L for neutrophil is calculated from total leukocyte count of 4.5×10^9 /L, according to formula on item 2 above. Lower limit of normal of 0.99×10^9 /L for lymphocytes is calculated from total leukocyte count of 4.5×10^9 /L. Above the lower limit of normal range values are used to classify CTCAE grade for neutrophil and lymphocyte counts.

Appendix E. Data Cutoff Date

Data cutoff date for each statistical summary or test will be determined and applied.

Appendix F. Hepatic and Renal Function

Hepatic Function based on National Cancer Institute Organ Dysfunction Working Group Classification of Hepatic Dysfunction: 10-13

	Bilirubin (mg/dL)	AST (IU/L)
Normal	≤ 1.0	≤ 40
Mild Impairment	≤ 1.0	> 40
Moderate Impairment	$> 1.0 \text{ and} \le 1.5$	Any
	$> 1.5 \text{ and } \le 3.0$	Any
Sever Impairment	> 3.0	Any

Renal Function based on FDA guidance for industry Pharmacokinetics in Patients with Impaired Renal Function – Study Design, Data Analysis, and Impact on Dosing and Labeling:

	CrCL (mL/min)
Normal	≥ 90
Mild Impairment	60 ≤ CrCL< 90
Moderate Impairment	30 ≤ CrCL< 60
Sever Impairment	CrCL < 30

If serum creatinine is in μmol/L, it can be converted to mL/min following:

$$\mathit{CrCL} = \frac{(140-age) \times (weight\ in\ kg) \times (1.23\ if\ male, 1.04\ if\ female)}{\mathit{serum\ creatinine\ in\ } \mu mol/L}$$

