5 STUDY ACTIVITIES

5.1 Eligibility Criteria

A subject will be eligible for study participation if he/she meets the following criteria within 28 days prior to the first day of study drug administration.

Consent

1. Subjects or their legally authorized representative (if permitted per local regulations) must be capable of understanding and complying with parameters as outlined in the protocol and must voluntarily sign and date an informed consent, approved by an independent ethics committee (IEC)/institutional review board (IRB), prior to the initiation of any screening or study-specific procedures.

Demographic and Laboratory Assessments

- 2. Adult individuals ≥ 18 years old.
- 3. Subject must meet the following laboratory parameters, per laboratory reference range within the screening period prior to study drug administration:
 - creatinine clearance ≥ 30 mL/minute; calculated by the Cockcroft Gault formula or measured by 24-hour urine collection;
 - bilirubin < 3.0 × upper limit of normal (ULN) (adequate liver function) for Part 1, or bilirubin < 2.0 × ULN for Part 3;
 - absolute neutrophil count (ANC) ≥ 1,500/µL;
 - platelets ≥ 100,000/μL.
- 4. Subject is willing and able to comply with procedures required in this protocol.

Disease Activity

- 5. Diagnosis of newly diagnosed AML.
- 6. Subject meets the following disease activity criteria:
 - confirmation of AML by the WHO criteria (2016)
 - confirmation of CR or CRi following completion of intensive Induction and Consolidation chemotherapies (note: additional consolidation therapy on-study will be considered a protocol violation)
 - subject should be within one of the following time windows:
 - achieved first CR or CRi (after induction) within 120 days of the first dose of study drug (Cycle 1 Day 1), or

- be no more than 75 days since last dose of intensive conventional (including both induction and consolidation) chemotherapies until enrollment (Cycle 1 Day 1)
- AML has intermediate or poor risk cytogenetics per National Comprehensive Cancer Network (NCCN) 2016 criteria (Appendix E)⁴²
- \bigcirc 7. Eastern Cooperative Oncology Group (ECOG) performance status of ≤ 2.

Subject History

- 8. No history of APL.
- 9. No history of active central nervous system involvement with AML.

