7.1 Demographics and Baseline Characteristics

All demographics and baseline disease characteristic summary statistics and analyses are based on the latest one collected prior to the first dose of study drug or date of randomization for untreated subjects. The following demographic and baseline disease characteristics will be summarized:

Demographics:

- age (years) and age categories (< 60 years, ≥ 60 years)
- gender (male/female)
- race (white, black or African American, Asian, and other)
- region (
 , or other regions
 requested by regulatory agencies)
- height (cm)
- weight (kg)

[figure not shown]
Baseline Disease-Related Characteristics:

- AML type (De Novo, Secondary AML)
- Secondary AML (Post MDS/CMML/AML, Therapy-related AML)
- Previous treatment with venetoclax (Yes, No)
- Previous treatment with AZA (Yes, No)

- MRD status prior to randomization ($\geq 10^{-3}$, $< 10^{-3}$, Unknown/Missing)
- NCCN cytogenetic risk (Intermediate, Poor)
- Best response after conventional Induction chemotherapy prior to randomization (CR, CRi)
- Best response after conventional Consolidation chemotherapy prior to randomization (CR, CRi)
- Number of Consolidation cycles (1 cycle, 2 cycles, 3 cycles, > 3 cycles)
- ECOG performance status (0, 1, 2)
- Molecular marker at diagnosis (FLT3, IDH1/2, TP53, NPM1, if data is available)
- Hepatic impairment (Yes, No)
- Renal impairment (Yes, No)
- Stratification factor: relapse risk (poor risk cytogenetic or MRD-positive $(\geq 10^{-3})$, others)
- Bone marrow blast count at diagnosis (< 30%, $\ge 30\%$ < 50%, $\ge 50\%$)
- Bone marrow blast count at diagnosis (%)
- NCI CTC (National Cancer Institute Common Terminology Criteria, version 5.0) grade of neutropenia at baseline
- Neutrophils value at baseline ($\times 10^9/L$)
- NCI CTC grade of thrombocytopenia at baseline
- Platelet count at baseline ($\times 10^9/L$)
- NCI CTC grade of anemia at baseline
- Hemoglobin value at baseline (G/L)

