9.3 Analysis of Laboratory Data

Unless otherwise specified, analysis of laboratory data will include post-baseline measurements within 30 days of the last dose of the study drug for Arm A or Part 1 or within 30 days of the end of Cycle 24, disease relapse, or study discontinuation whichever is the earliest for subjects in Arm B.

Data collected from central and local laboratories, including additional laboratory testing due to an SAE, will be used in all analyses. The clinical laboratory tests defined in the protocol operations manual (e.g., hematology and clinical chemistry) will be summarized. Change from baseline will be summarized and presented for each lab test at scheduled post-baseline visits defined in Appendix C. Baseline is defined as the last non-missing observation before the first administration of study drug or randomization if no study drug is given.

For shifts relative to National Cancer Institute Common Toxicity Criteria for Adverse Events (NCI CTCAE version 4.03), baseline and post-baseline laboratory observations will be categorized as grade 0, grade 1, grade 2, grade 3, or grade 4 according to NCI CTCAE grade version 4.03. The baseline grade is defined as the grade of the last measurement collected on or prior to the first dose of study drug (or randomization for non-treated subjects). In cases where multiple values are collected on the same day, the maximum grade value will be selected as the value for that day. The maximum NCI toxicity grade value is the value with highest NCI toxicity grade collected after the first dose of study drug.

For each lab test, cross tabulate will be generated for the number of subjects with baseline values of grade 0, grade 1, grade 2, grade 3, grade 4, or missing grade versus maximum post-baseline values of grade 0, grade 1, grade 2, grade 3, grade 4, or missing grade. All subjects in the safety analysis set will be included in the cross tabulation regardless whether baseline or post-baseline measurements are collected.

The separate laboratory shifts tables based on the two criteria below will be generated for each laboratory tests related to CTCAE:

- 1. Shifts from grade 0 (normal) at baseline to grade 1 4 post-baseline (maximum) and worsening from an abnormal baseline value of at least one grade up post-baseline (maximum)
- 2. Shifts from grade 0 2 at baseline to grade 3 or 4 post-baseline (maximum) and from grade 3 at baseline value to grade 4 post-baseline (maximum).

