9.4 Safety Subgroup Analyses

Safety analyses described in Section 9.2 (adverse events) may be summarized for the subgroups including, but not limited to, those defined below:

- Age $(< 60, \ge 60)$
- Gender (Male, Female)
- region (
 , or other regions requested by regulatory agencies)
- Hepatic impairment at baseline (Yes, No)

• Renal impairment at baseline (Yes, No)

Definition of hepatic impairment at baseline and renal impairment at baseline are described in Appendix F.

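### SAP Appendix F defines hepatic impairment by fixed bilirubin and AST values, not multiples of each laboratory's ULN, so subjects can be misclassified in either direction

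*SAP*

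**What the plan says.** **SAP Appendix F** gives the classification under the title "Hepatic Function based on National Cancer Institute Organ Dysfunction Working Group Classification of Hepatic Dysfunction". Its bilirubin column is in mg/dL, with cuts at 1.0, 1.5 and 3.0. Its AST column is in IU/L, with one cut at 40. A subject is normal only with bilirubin at or below 1.0 and AST at or below 40. No ULN appears in the hepatic table.

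**Where it is used.** SAP 7.1 lists hepatic impairment as a Yes/No baseline characteristic, and SAP 7.0 has the baseline tables produced for Part 1 by dose level. SAP 9.4 lists it as a safety subgroup: "Definition of hepatic impairment at baseline and renal impairment at baseline are described in Appendix F". The wording of 9.4 makes these subgroup summaries optional. SAP 8.6 also lists it as an efficacy subgroup.

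**How liver function is judged elsewhere.** Protocol 5.1 requires "bilirubin < 3.0 × upper limit of normal (ULN) (adequate liver function) for Part 1, or bilirubin < 2.0 × ULN for Part 3", and its lead-in reads "Subject must meet the following laboratory parameters, per laboratory reference range within the screening period". The Hy's law criterion in Protocol 6.3 uses AST or ALT at or above 3 × ULN with bilirubin at or above 2 × ULN. The Hy's law summary in SAP 9.3 also uses multiples of ULN.

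**Whose laboratories.** The schedule in Protocol Appendix H puts clinical chemistry under local laboratory values. SAP 9.3 states: "Data collected from central and local laboratories, including additional laboratory testing due to an SAE, will be used in all analyses". The synopsis gives about 250 sites in about 17 countries.

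**The concern.** A fixed cut-off agrees with a laboratory's own reference range only if that laboratory's ULN equals the cut-off. Appendix F therefore behaves as if every contributing laboratory had a ULN of 1.0 mg/dL for bilirubin and 40 IU/L for AST. Nothing in the documents says so, and the ULN-based rules elsewhere suggest that ranges were expected to differ.

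At stake is the meaning of a Yes/No variable whose Yes group is likely to be small. If laboratory-normal subjects enter it, or abnormal subjects leave it, the contrast in adverse events between Yes and No is blurred. The SAP also does not say which Appendix F categories make a Yes, so two programmers could build different subgroups from the same data.

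**Working it through.** The plan states no figure here to reproduce. The check has two steps.

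**Step 1: direction of error.** Apply the Appendix F cuts, count anything other than normal as impaired, and compare with bilirubin ≤ ULN and AST ≤ ULN. All ULNs are assumptions, because the documents give none.

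| Assumed ULN | Result |
|---|---|
| Bilirubin 1.0 mg/dL, AST 40 IU/L | No disagreement |
| Bilirubin 1.2 | Values above 1.0 up to 1.2 are laboratory-normal but impaired in Appendix F |
| AST 45 | AST 41 to 45 is laboratory-normal but impaired (AST-only row) |
| AST 35 | AST 36 to 40 is abnormal but called normal when bilirubin ≤ 1.0 |
| Bilirubin 0.9 | Values above 0.9 up to 1.0 are abnormal but called normal when AST ≤ 40 |

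The error runs both ways. Replacing 1.0 and 40 by the laboratory's ULN removes all of it.

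**Step 2: illustrative size for bilirubin.** Inputs: 66 Part 1 subjects (Protocol 4.1). Assumptions: bilirubin is lognormal with median 0.5 or 0.6 mg/dL, the ULN is its 97.5th percentile, all subjects share one ULN, and the row from above 1.0 to 1.5 mg/dL counts as impaired.

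- log-SD = ln(ULN / median) / 1.96
- P = Pr(bilirubin > 1.0) = 1 − Φ(ln(1.0 / median) / log-SD)
- laboratory-normal but above 1.0 = P − 2.5%, and the number of subjects = 66 × (P − 2.5%)

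Example with ULN 1.2 and median 0.5: log-SD = 0.8755 / 1.96 = 0.447; z = 0.6931 / 0.447 = 1.55; P = 6.0%; 66 × (6.04% − 2.5%) = 2.3 subjects.

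| ULN | Median | P | Above 1.0, of 66 | Of these, laboratory-normal | Share |
|---|---|---|---|---|---|
| 1.0 | 0.5 or 0.6 | 2.5% | 1.65 | 0 | 0% |
| 1.1 | 0.5 | 4.2% | 2.80 | 1.15 | 41% |
| 1.1 | 0.6 | 4.9% | 3.25 | 1.60 | 49% |
| 1.2 | 0.5 | 6.0% | 3.98 | 2.33 | 59% |
| 1.2 | 0.6 | 7.4% | 4.90 | 3.25 | 66% |
| 1.3 | 0.5 | 7.7% | 5.12 | 3.47 | 68% |
| 1.3 | 0.6 | 9.8% | 6.45 | 4.80 | 74% |

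At a ULN of 0.9 the sign flips. P is 1.0% (median 0.5) or 0.7% (median 0.6), so 2.5% − P of the 66, about 1 subject, has bilirubin above the laboratory's ULN but not above 1.0 mg/dL.

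The last column is a share of subjects with bilirubin above 1.0, not of the whole Yes group. If raised AST alone also makes a Yes, the group is larger and the share changes by an amount that cannot be estimated here.

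**The case against.** Entry limits and DLT criteria serve a different purpose from a descriptive subgroup. A fixed classification is stated and reproducible, and it contradicts no other section. That stands: this is a weak definition, not a conflict between rules.

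The size rests on invented inputs. The documents give no ULN. The 2.5% above ULN is a healthy-population figure applied to patients shortly after intensive chemotherapy, and ULNs of 1.1 to 1.3 explore one direction only. That also stands, so the counts are illustrative.

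Three stronger readings are tempting, and the documents do not support them.

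- **That subjects with normal liver tests are in fact labelled impaired.** This needs a bilirubin ULN above 1.0 or an AST ULN above 40. Neither is documented, and lower ULNs reverse the error.
- **That Appendix F calls eligible Part 1 subjects severely impaired, in a row that should be empty.** At an assumed ULN of 1.2 the entry limit is 3.0 × 1.2 = 3.6 mg/dL, so values of 3.1 to 3.5 would fall in the top row. They are about 2.6 to 2.9 × ULN, hence not normal on either scale, and the planned Yes/No summaries do not change. Nor need the row be empty after rescaling. Eligibility uses the screening period, baseline is the latest value before first dose (SAP 7.1), and chemistry is repeated on Day 1.
- **That a real excess of toxicity would be hidden.** With only about 3 to 6 subjects above 1.0 mg/dL in the illustration, the bilirubin-defined group could not reliably show or exclude an excess under either definition.

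The category labels in the Appendix F table may have been displaced when the PDF was read, so nothing is made of which label the row from above 1.0 to 1.5 carries. The count does depend on whether that row is a Yes. If Yes means moderate or worse and that row is mild, the 1 to 5 subjects drop out.

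**Conclusion.** The point holds as a low-priority weakness of definition. Appendix F is not scaled to laboratory ULN, the chemistry comes from local laboratories, and misclassification can follow in either direction wherever a ULN differs from 1.0 mg/dL or 40 IU/L. The true size is unknown. It is zero for bilirubin at a ULN of 1.0, and about 1 to 5 of 66 Part 1 subjects at assumed ULNs of 1.1 to 1.3 mg/dL, given the lognormal assumption and a Yes that includes the row from above 1.0 to 1.5 mg/dL. The effect of AST is not quantified.

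The reach is narrow: the Part 1 baseline table and the optional safety subgroup of SAP 9.4. The efficacy subgroup in SAP 8.6 was written for the randomized comparison in Part 2, which has been removed from the protocol. The DLT endpoint, dose decisions and eligibility do not use this variable.

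**What to change.** In SAP Appendix F, replace the fixed values by multiples of the reporting laboratory's ULN:

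- bilirubin: ≤ ULN; > 1.0 to ≤ 1.5 × ULN; > 1.5 to ≤ 3.0 × ULN; > 3.0 × ULN
- AST: ≤ ULN or > ULN

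Add one sentence stating which categories count as Yes for hepatic impairment, and in particular whether raised AST alone does. Use the same variable in SAP 7.1 and 9.4.

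The cost is a short SAP text change and one re-derived variable. The laboratory ULNs are already needed for eligibility and for the Hy's law summary, and no new data are collected. Protocol 7.1 has the SAP finalized before database lock, so the change belongs before then.
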